5.2. Study population

The study population will be derived from individuals aged 10-50 years with asymptomatic *P. falciparum* malaria infection who agree to be screened for malaria infection.

For the randomised trial, we will aim to recruit 100 individuals. Eligible individuals will have microscopically detectable *P. falciparum* gametocyte densities of ≥ 16 gametocytes/ μL .

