7.2. Secondary outcome measures

- Median within person percent change (presented as percent reduction) in mosquito infection rate from baseline to all feeding time-points, with comparison within and between arms.
- Median mosquito infection rate at all feeding time-points, with comparison within treatment arms compared to baseline, and between arms.
- Infectivity to mosquitoes at all feeding time-points, with comparison within treatment arms compared to baseline, and between arms.
- Mean oocyst intensity (in all/all infected mosquitoes) at all feeding time-points, with comparison within treatment arms compared to baseline, and between arms.
- Male and female gametocyte prevalence at all time-points, determined by microscopy or molecular assays, with comparison within treatment arms compared to baseline, and between arms.
- Male and female gametocyte density at all time-points, determined by microscopy or molecular assays, with comparison within treatment arms compared to baseline, and between arms.
- Male and female gametocyte sex ratio (proportion male) at all time-points, determined by microscopy or molecular assays, with comparison within treatment arms compared to baseline, and between arms.
- Gametocyte circulation time (cumulative), determined by microscopy or molecular assays, compared between treatment arms.
- Gametocyte area under the curve (cumulative), determined by microscopy or molecular assays, compared between treatment arms.
- Asexual and total parasite prevalence at all time-points, determined by microscopy or molecular assays, with comparison within treatment arms compared to baseline, and between arms.
- Asexual and total parasite density at all time-points, determined by microscopy or molecular assays, with comparison within treatment arms compared to baseline, and between arms.
- Haemoglobin density at all time-points, with comparison within treatment arms compared to baseline, and between arms.
- Median within person percent change (presented as percent reduction) in haemoglobin density from baseline to all time-points, with comparison within and between arms.
- The frequency and prevalence of adverse events (all AE's, treatment related AE's, and haematological AE's) observed up to and including day 2, 7, and 14 post-treatment, and at all timepoints.

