11.1. Analysis plan

Mosquito infectivity will be assessed at three levels: the mean number of oocysts in a sample of mosquitoes (i.e. oocyst intensity), the proportion of mosquitoes infected with any number of oocysts (i.e. mosquito infection rate), and the infectivity of the study participant to any number of mosquitoes (i.e. infectivity to mosquitoes). The primary outcome measure will be the percent change in mosquito infection rate within each arm by day 2 compared to baseline, with other time-points of infectivity assessments as secondary outcomes. Percent change will be reported as percent reduction (with 100% as total reduction of transmission, and negative values as enhanced transmission). Other secondary transmission outcomes are as described in the 'Objectives' section above. Some exploratory objectives may be published separately from the main primary/secondary outcomes.

Statistical analysis will be conducted using the most recent STATA and SAS versions (16.0 and SAS version 9.4 at time of writing). Mosquito infection data will be analysed at time-points after baseline only for those individuals who are infectious at baseline, although the data and analyses from all enrolled individuals will be published in the appendix for completeness. Individuals will be classified as infectious to mosquitoes if they infect at least 1 mosquito, with any number of oocysts. Infectivity to mosquitoes and parasite/gametocyte prevalence will be compared within and between treatment arms using generalised linear models (family: binomial, z-score, co-efficient with 95% CI) or fishers exact tests. Absolute haemoglobin density and percent change in haemoglobin density (relative to baseline) will be compared using paired t-tests (t-score for difference compared to day 0) and two-way t-tests (t-score for difference between ACT matched treatment groups at each time-point). The proportion of gametocytes that are male will be calculated for all values with total gametocyte densities of 0.2/ μ L and over. Gametocyte circulation time will be calculated to determine the average period (in days) that a mature gametocyte circulates in the blood prior to clearance, using a deterministic compartmental model that assumes a constant rate of clearance and has a

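### Within-arm tests of binary outcomes against baseline use unpaired methods, and where baseline is 100% by selection the usual logit GLM cannot give the promised coefficient and CI

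*Protocol*

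**What the plan says.** Protocol section 7.2 lists, among the secondary outcomes, "Infectivity to mosquitoes at all feeding time-points, with comparison within treatment arms compared to baseline, and between arms". It asks for the same two comparisons for male and female gametocyte prevalence and for asexual and total parasite prevalence.

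Section 11.1 gives one method for all of these: "Infectivity to mosquitoes and parasite/gametocyte prevalence will be compared within and between treatment arms using generalised linear models", specified as "family: binomial, z-score, co-efficient with 95% CI) or fishers exact tests". It names no paired test, participant effect or clustered standard error for them.

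Two further rules fix the baseline value:

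- **Infectivity.** "Mosquito infection data will be analysed at time-points after baseline only for those individuals who are infectious at baseline", where "Individuals will be classified as infectious to mosquitoes if they infect at least 1 mosquito, with any number of oocysts". The sentence that sets the restriction adds: "although the data and analyses from all enrolled individuals will be published in the appendix for completeness".
- **Gametocytes.** Section 5.2 requires microscopically detectable "gametocyte densities of ≥ 16 gametocytes" per microlitre for entry.

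For other outcomes section 11.1 does respect the repeated measures. It uses paired t-tests for haemoglobin, signed-rank tests against matched day 0 values for remaining quantitative data, and a random effect for gametocyte circulation time.

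**The concern.** There are two separate problems.

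1. **Pairing.** Day 0 and each later day are measured on the same people. Fisher's exact test treats 18 people seen twice as 36 independent people.
2. **A fixed reference.** If only people positive at baseline are analysed, the baseline proportion is n/n whatever the data. Change can only be downward, and a logit model has no finite estimate for the contrast. The reference is also somewhat unfair: a person who infected at least one mosquito at day 0 may infect none at the next feed by chance alone.

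At stake are the within-arm p-values and intervals for named secondary outcomes. The choice between GLM and Fisher also matters. With 8 of 20 people turning negative, the logit GLM reports p = 0.999 and Fisher reports p = 0.003, and the protocol gives no rule for choosing between them.

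**Working it through.** **The plan's own figure.** The protocol gives no figure for these tests. Its one power figure (section 5.4, 88%) concerns the reduction in mosquito infection rate. A simulated random-intercept logistic model (20 participants, 50 mosquitoes, ICC 0.5 on the latent scale, odds ratio 0.1 tested against 0.2, 17% as a population average) gave 88.5%, so the planning inputs are usable below.

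**Inputs.** From the protocol: 20 per arm, 50 mosquitoes per feed, baseline 17%, ICC 0.5 (section 5.4); significance at p < 0.05 (section 11.1), taken as two-sided. Assumed: n = 18 as an illustrative number infectious at baseline, since about 91% of 20 is 18.2 (step 3).

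**Step 1: logit GLM with a full baseline cell.** If k of n turn negative, the coefficient is log[(n-k)/k] - log[n/0], which is minus infinity. Software stops at an arbitrary value. For 20/20 against 12/20 it returns -23.2 with SE 17,768 and p = 0.999. A clustered standard error would not help, because the coefficient itself does not exist.

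**Step 2: Fisher against a paired test.** All discordant pairs run one way, so:

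- Fisher, two-sided: p = 2 x C(n,k) / C(2n,k)
- exact McNemar: p = 2 x 0.5^k

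Example, n = 20, k = 5: 2 x 15,504 / 658,008 = 0.047, against 2 x 0.03125 = 0.0625.

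| k negative | Fisher, n = 18 | Fisher, n = 20 | exact McNemar |
|---|---|---|---|
| 4 | 0.104 | 0.106 | 0.125 |
| 5 | 0.045 | 0.047 | 0.0625 |
| 6 | 0.019 | 0.020 | 0.031 |
| 8 | 0.003 | 0.003 | 0.008 |

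Fisher's p is the smaller in every row, because each factor (n-i)/(2n-i) is below one half for i of 1 or more. The two fall on opposite sides of 0.05 only at k = 5.

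**Step 3: does this produce false positives?** Let q be a person's infection probability, with logit(q) normal around logit(p0) and variance 3.29 (which gives ICC 0.5). With no drug effect:

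- infectious at baseline: A = E[1 - (1-q)^50]
- of those, negative at the next feed: B = E[{1 - (1-q)^50}(1-q)^50] / A
- type I error: the probability that Fisher gives p < 0.05 when n is Binomial(20, A) and k is Binomial(n, B)

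| Median baseline rate p0 | A | B | Fisher type I error |
|---|---|---|---|
| 17% (section 5.4, as the typical participant) | 91% | 4.9% | 0.15% |
| 8.4% (if 17% is the population average) | 83% | 8.7% | 1.2% |
| 5% (assumption) | 75% | 12.3% | 3.2% |
| 3% (assumption) | 67% | 16.4% | 6.0% |
| 1% (assumption) | 47% | 27.4% | 10.4% |

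Adding feed-to-feed variation at p0 = 17% (assumed SD 0.5 or 1.0 on the logit scale) raises the error to only 0.3% or 0.8%. In the all-enrolled set, Fisher's error was 0.07% to 0.3% across all baseline rates tried.

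**The case against.** The strongest reply has four parts.

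- **The flip depends on the paired test chosen.** At k = 5 the mid-p McNemar value is 0.031 and the asymptotic value 0.025, both agreeing with Fisher. At k = 4 the asymptotic McNemar value is 0.0455 while Fisher gives 0.104 to 0.106, so the unpaired test can be the less favourable one. This stands, so the p-value argument alone is weak.
- **The link is not named.** For 18/18 against 13/18 a log link gives -0.325 (SE 0.146) and an identity link -0.278 (SE 0.106). Both are finite, though the fit sits on the boundary, and the log link fails if everyone turns negative. The GLM failure is therefore a property of the usual logit link, not of every binomial GLM.
- **Baseline is not always 100%.** It is free for asexual parasite prevalence, for sex-specific prevalence by molecular assay, and for infectivity in the all-enrolled appendix analysis. There only the pairing is at issue.
- **Link and clustering can be left to an SAP.** That is fair for the GLM. It does not cover Fisher's test, which the protocol names for within-arm use and which is unpaired by definition.

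A reader might infer that the plan would systematically declare false losses of infectivity. The protocol's inputs do not support that: type I error stays well below 5%, exceeding it only at assumed median baseline rates of about 3% or lower.

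**Conclusion.** The point holds in limited form. For within-arm comparisons of binary outcomes with baseline, section 11.1 names methods that do not account for the same people being measured twice. In two settings it also promises a coefficient and CI that the usual logit GLM cannot produce: the main infectivity analysis, and total gametocyte prevalence by microscopy. The second assumes that the day 0 reading agrees with the screening film. The missing estimate is the firmest part, since it follows from the design rather than from the data.

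The size is modest. The change in p-values matters only at borderline counts (5 of 18 to 20), and only against exact McNemar. Large reductions are significant either way.

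It would be wrong to extend the point to the primary outcome or to the between-arm tests. Percent change in mosquito infection rate falls under the signed-rank rule, and Fisher's test or a GLM is appropriate between independent randomised arms.

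**What to change.** Amend the one paragraph in section 11.1:

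- **Where baseline is 100% by selection** (infectivity among those infectious at day 0; total gametocyte prevalence by microscopy): drop the within-arm GLM or Fisher test. Report n/N still positive at each day with an exact (Clopper-Pearson) 95% CI, and rely on the between-arm contrast for inference. For example, 15 of 20 still positive is 75%, CI 51% to 91%.
- **Where baseline is not fixed** (asexual parasite prevalence, sex-specific molecular prevalence, infectivity in all enrolled): use a paired method, such as exact McNemar or a logistic model with a participant random intercept or GEE.
- **Between arms:** keep the GLM or Fisher's exact test.

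McNemar should not be carried into the first group as a full remedy, because it handles the pairing but not the selection. A random-intercept logistic model has no finite day coefficient for microscopic gametocyte prevalence, because everyone is positive at baseline.

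The cost is a text change with no new data. A few borderline within-arm p-values become less favourable or are no longer reported.

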2. STUDY SYNOPSIS

Artemisinin Combination Therapies (ACT) are the first-line treatment for uncomplicated *Plasmodium falciparum* malaria. ACTs rapidly clear asexual *P. falciparum* parasites, responsible for clinical symptoms, but have limited activity against mature gametocytes, which are the only life stages capable of transmitting to mosquitoes. To reduce *P. falciparum* transmission, the World Health Organisation (WHO) recommends the addition of a single low dose of primaquine (0.25 mg/kg), a potent and fast-acting gametocytocidal drug, to ACT [1]. Although Artesunate-Amodiaquine (ASAQ) is a commonly used ACT, limited available data

suggest poor activity against gametocytes [2] and the added benefit of SLD PQ in combination with ASAQ remains unknown. We previously showed that Artemether-Lumefantrine (AL) is a more potent ACT in terms of gametocyte clearance and transmission reduction efficacy compared to Dihydroartemisinin-Piperaquine (DP) [3], [4] [NECTAR3, in preparation]. Recently, triple artemisinin-based combination therapies (TACT) such as Artemether-Lumefantrine plus Amodiaquine (ALAQ) have been proposed to delay the emergence of drug resistance and to provide efficacious treatment for multi-drug resistance *P. falciparum* infections [5], [6]. The transmission reducing efficacy of ALAQ or ALAQ-PQ has not yet been tested.

In this study we aim to determine transmission reducing efficacy of Artesunate-Amodiaquine (ASAQ) with and without a single low dose (0.25mg/kg) of Primaquine (SLD PQ) and Artemether-Lumefantrine (AL) with and without Amodiaquine (AQ) and Primaquine (PQ). To achieve this, we propose to conduct a five-arm, single-blind, randomised control trial to test the gametocytocidal and transmission-blocking efficacy of SLD PQ in combination with Artesunate-Amodiaquine and Artemether-Lumefantrine-Amodiaquine. Individuals will be recruited to an AL-only arm as an internal control for the ALAQ arm, and for comparison to recent trials at the same site [NECTAR3, in preparation]. Individuals who meet inclusion criteria will be randomised in a 1:1:1:1:1 ratio to: ASAQ, ASAQ-PQ, AL, ALAQ, ALAQ-PQ.

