4.2. Secondary specific objectives

- To assess differences in other mosquito infectivity parameters (mosquito infection rate, change in infection rate, infectivity to mosquitoes, and oocyst density) following treatment with ASAQ, ASAQ-PQ, AL, ALAQ and ALAQ-PQ in children and adults at all feeding timepoints compared to pre-treatment (day 0) and between treatment matched arms (ASAQ vs ASAQ-PQ, AL vs ALAQ, ALAQ vs ALAQ-PQ).
- To assess differences in gametocyte parameters (prevalence, density, circulation time, area-under-the-curve, sex-ratio) following treatment with ASAQ, ASAQ-PQ, AL, ALAQ and ALAQ-PQ in children and adults at all feeding timepoints compared to pre-treatment (day 0) and between treatment matched arms (ASAQ vs ASAQ-PQ, AL vs ALAQ, ALAQ vs ALAQ-PQ).
- To assess differences in safety parameters (AE frequency, Hb density, median drop in Hb) following treatment with ASAQ, ASAQ-PQ, AL, ALAQ and ALAQ-PQ in children and adults at all feeding timepoints compared to pre-treatment (day 0) and between treatment matched arms (ASAQ vs ASAQ-PQ, AL vs ALAQ, ALAQ vs ALAQ-PQ).
- To assess differences in biochemical parameters (ALT, CBC, Creatinine) following treatment with ASAQ, ASAQ-PQ, AL, ALAQ and ALAQ-PQ in children and adults at all feeding timepoints compared to pre-treatment (day 0) and between treatment matched arms (ASAQ vs ASAQ-PQ, AL vs ALAQ, ALAQ vs ALAQ-PQ).

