5.1. Study site

The Malaria Research and Training Centre (MRTC) in Bamako, Mali will use the field site of Ouelessebougou for recruitment. The MRTC has the unique position of being one of very few sites in Africa that can study malaria transmission endpoints. Since 2013 the MRTC successfully carried out similar trials at this site with great success, in collaboration with the University of California San Francisco, the London School of Hygiene and Tropical Medicine and the Radboud University Medical Center, Nijmegen, the Netherlands. In the 2013-2014 study, the MRTC demonstrated the efficacy of SLD PQ of doses of 0.125mg/kg or greater in combination with dihydroartemisinin-piperaquine for blocking *P. falciparum* transmission safely in G6PD normal Malian males from the age of 10-50 years [8]. MRTC has already established all the assays required for the study described in this protocol.

The MRTC is experienced in conducting Good Clinical Practice (GCP) compliant clinical trials including phase 1, 2, 3 and 4 of malaria vaccine and drug studies. Ouelessebougou village has been conducting ongoing clinical research since 2008 and is endemic for malaria with marked seasonality and a high burden of malaria in both children and adult populations. In recent years the prevalence of *P. falciparum* malaria in children under 5 years of age has ranged between 14% and 54% during the transmission season. The frequency of G6PD deficiency is in the range of 10 to 15%.

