7.3. Exploratory outcomes

- Parasite genotype and transcriptional analysis at baseline and at post-treatment timepoints, both for blood stage parasites and oocysts.
- Plasma biomarkers (antibodies and parasite protein) at baseline and at post-treatment timepoints.
- Association between gametocyte density and mosquito infection rates per study drug and time-point, to examine evidence for loss in gametocyte fitness/sterilization.
- Human genotype analysis at baseline (G6PD, CYP2D6, HBB)
- ALT/Creatine density at all time-points with comparison within treatment arms compared to baseline, and between arms.
- Gametocyte density, mosquito infection rate and mean oocyst intensity before and after MACS, for within treatment arm comparison to baseline and comparison between treatment arms.

Table 5. Outcome measures

Outcome measure	Day 0	Day 1	Day 2	Day 7	Day 14	Day 21	Day 28
Mosquito infectivity	*		*	*	*	**	**
Asexual parasite prevalence & density	*		*	*	*	*	*
Gametocyte prevalence, density, sex ratio, genotype	*		*	*	*	*	*
Biochemistry (ALT/Creatinine)	*		*		*		
CBC	*		*		*		
Haemoglobin	*	*	*	*	*	*	*
Safety assessment: signs of haemolysis	*	*	*	*	*	*	*
Safety assessment: Adverse Events	*	*	*	*	*	*	*
Plasma biomarkers	*		*	*	*	*	*
Mosquito infectivity after MACS	*		*				

** Mosquito infectivity assays will be performed at day 21 for any individuals infectious at day 7 or 14; and at day 28 for any individuals infectious at day 14 or 21.

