8.2. Study procedures

Participants who agree to participate and provide written, informed consent will be assessed for the presence of sexual blood stage parasite with a thick blood film. Individuals with ≥ 16 gametocytes/ μL will go through additional screening for eligibility including haemoglobin measurement, CBC, assessment of the renal and liver functions and pregnancy tests. Recruitment will continue until 100 infected individuals with microscopically detectable *P. falciparum* gametocytes ($\geq 16/\mu\text{L}$) are recruited and randomised. Individuals with symptomatic malaria will not be enrolled in the study and will be treated with artemether + lumefantrine, the standard treatment for uncomplicated malaria as per the Ministry of Health policy in Mali. Individuals screened found with other acute diseases will also be treated according to the standard of care in Mali. Those with chronic disease will be referred to the district hospital for further evaluation and management.

Eligible patients will then be randomized (see below under randomization procedure) to one of the treatment groups, and drugs will be administered. In case of vomiting within 30 minutes after drug intake, the drugs will be re-administered once.

The participants will be compensated for any travel costs and for work loss income. Participants will be followed for 28 days as described in **Table 6** (below). Single venous draws or finger pricks will be used.

Any individuals determined to have an adverse event (haemolytic or otherwise) will be treated in accordance with national guidelines and best practice and will be withdrawn from the study at the discretion of the study clinician.

Table 6. Sampling framework for study participants

Required vacutainer	Time of sampling (d = day)	Required volume (mL)	Day 0	Day 1	Day 2	Day 7	Day 14	Day 21	Day 28
			V	C	V	V	V	V	V
Heparin (2-5mL)	Mosquito infectivity	2	*		*	*	*	**	**

	MACS	3	*		*				
EDTA (0.05-3.4mL)	Blood in RNA protect for RNA analysis/parasite genotyping	0.7	*		*	*	*	*	*
	Blood smear for asexual parasite and gametocyte density	0.1	*		*	*	*	*	*
	Filter paper blood spots	0.05	*		*	*	*	*	*
	Haemoglobin	0.05	*	*	*	*	*	*	*
	Plasma	1	*		*	*	*	*	*
	CBC	0.5	*		*	*	*		
	Human genotyping	1	*						
SST (0.8 mL)	Biochemistry	0.8	*		*	*	*		
	Maximum total Volume of blood sampled (mL)	38.65	9.2	0.05	9.2	6.2	6.2	3.9	3.9

\$ V denotes venous blood sampling and C denotes capillary sampling from a finger prick.

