9. SAFETY EVALUATION

The major safety endpoint is haemolysis. For this reason, haemoglobin will be measured before treatment, at days 1, 2, 7, 14, 21, and 28. Previous studies have shown that highest haemoglobin fall related to drug induced haemolysis can be detected within 7 days after treatment. In addition at 24 hours, and subsequent days of follow up, a questionnaire

assessing adverse events (AE) will be carried out. All participants will have access to contact study medical staff 24 hours a day and medical facilities that can give safe blood transfusions. Participants who require blood transfusions will be hospitalised at the district hospital in Ouelessebougou or referred to the University hospitals in Bamako for proper management. Additional safety precautions due to the small risk of transient haemolysis in this population will include the performance of clinical examinations and monitoring for adverse events (AE) at all sampling time points, carefree of charge to all participants throughout the duration of follow-up.

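### Haemoglobin, the measure of the major safety endpoint, is compared by 20 vs 20 t-tests with no baseline-adjusted model and no use of G6PD genotype, so a fall confined to deficient participants reaches the arm mean at 10–15% of its size

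*Protocol*

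**What the plan says.** Section 9 states: "The major safety endpoint is haemolysis". Haemoglobin is measured before treatment and on days 1, 2, 7, 14, 21 and 28.

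Section 11.1 fixes the analysis. "Absolute haemoglobin density and percent change in haemoglobin density (relative to baseline) will be compared using paired t-tests" against day 0 within arm, and by "two-way t-tests (t-score for difference between ACT matched treatment groups at each time-point") between arms. Section 4.2 defines the comparisons as "between treatment matched arms (ASAQ vs ASAQ-PQ, AL vs ALAQ, ALAQ vs ALAQ-PQ"). The first and third of these isolate PQ. Table 1 gives 20 participants per arm.

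On G6PD:
- Section 5.1: "The frequency of G6PD deficiency is in the range of 10 to 15"%.
- The synopsis says enzyme status is not tested, so deficient people can be randomised to PQ.
- Section 12.2.2 places PQ haemolysis in deficient people.
- Section 7.3 lists "Human genotype analysis at baseline (G6PD, CYP2D6, HBB") as an exploratory outcome. The human-genomics objective in section 4.3 links genotype to parasite measures only.

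Individual-level safety is also covered. Section 9.3 reports Hb falls of more than 40% separately because of their possible link to PQ, section 7.2 makes haematological adverse events (AEs) a secondary outcome, Table 5 has signs of haemolysis assessed at every visit, and section 9.6 sends AEs and Hb up to day 14 to the DSMB. Section 8.2 says that a participant with an AE, haemolytic ones included, "will be withdrawn from the study at the discretion of the study clinician".

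**The concern.** The stated test does not match the stated risk. If PQ lowers Hb mainly in deficient participants, the information sits in two or three people per arm, and a comparison of arm means spreads it over 20. The genotype that would show where the falls occurred is collected but enters no stated Hb analysis.

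The t-tests also use baseline Hb less efficiently than they could. Section 11.1 gives gametocyte AUC a regression with and without baseline adjustment, but gives the major safety endpoint none.

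At stake is how a non-significant Hb comparison would be read: it could be taken as reassurance that the design cannot give. Chance imbalance in the number of deficient participants between matched arms could also hide or create a difference, and the planned test would not show it.

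**Working it through.** **The plan's own figure.** The only power figure is 88% in section 5.4, for mosquito infectivity. Simulating that model gives 87–89% when the 17% baseline is read as a population average, and 96–97% when it is read as the rate for the average participant. It gives no support to the Hb comparison, for which no power is stated.

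**From document figures alone** (n = 20 per arm, prevalence q = 0.10 to 0.15):
- Expected deficient participants per arm: 20q = 2 to 3.
- Probability of none in an arm: (1 − q)^20 = 12% to 4%. Probability of at most one: 39% to 18%.
- Probability that two matched arms differ by at least 2 deficient participants (difference of two binomials): 42% to 50%.
- A fall d in deficient participants shifts the arm mean by q × d, that is 10–15% of d.
- Detectable difference at 80% power, two-sided 0.05 (the protocol gives 0.05 without sidedness): 0.91 SD for 20 vs 20, and 0.63 SD for 40 vs 40.

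**Power, on assumed values.** The protocol gives no Hb SD, baseline correlation r or size of fall. The calculation is in g/dL, with change in g/dL standing in for percent change. SE = s√(2/n), with s = SD for absolute Hb, SD√(2(1 − r)) for change and SD√(1 − r²) for the baseline-adjusted model. Power is from the noncentral t.

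*General difference of 0.6 g/dL* (assumed SD 1.2–1.5, r 0.6–0.8). The low end is SD 1.5, r 0.6; the high end is SD 1.2, r 0.8.

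| Analysis | s (low / high end) | 0.6/SE | Power |
|---|---|---|---|
| Absolute Hb, 20 vs 20 | 1.50 / 1.20 | 1.26 / 1.58 | 23–34% |
| Change, 20 vs 20 | 1.34 / 0.76 | 1.41 / 2.50 | 28–68% |
| Baseline-adjusted, 20 vs 20 | 1.20 / 0.72 | 1.58 / 2.64 | 34–73% |
| Baseline-adjusted, pooled 40 vs 40 | 1.20 / 0.72 | 2.24 / 3.73 | 60–96% |

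Adjusted variance relative to change-score variance is (1 − r²)/(2(1 − r)) = (1 + r)/2, so adjustment alone gains little. Most of the last row comes from doubling n.

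*Fall of 2 g/dL in deficient participants only* (assumed SD 1.3, r 0.7). The mean shift is 2q = 0.2 to 0.3, and the PQ-arm variance rises by 4q(1 − q) = 0.36 to 0.51.
- Planned change test, 20 vs 20: s² = 1.69 × 0.6 = 1.014. At q = 0.10, SE = √((1.014 + 1.374)/20) = 0.346, ratio 0.58, power 9%. At q = 0.15, SE = √((1.014 + 1.524)/20) = 0.356, ratio 0.84, power 13%.
- Pooled and adjusted, 40 vs 40: s² = 1.69 × 0.51 = 0.862. At q = 0.10, SE = √((0.862 + 1.222)/40) = 0.228, ratio 0.88, power 14%. At q = 0.15, SE = √((0.862 + 1.372)/40) = 0.236, ratio 1.27, power 24%.

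A second set of assumptions, on the percent-change scale (10-point fall, SD 7.5 points), agrees: 7–9% for 20 vs 20 and 9–13% pooled. Across falls of 5–20 points and SDs of 5–10 points, the ranges are 5–26% and 6–46%.

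**The 40% rule.** At the entry minimum of 10 g/dL, 40% is 4 g/dL. A 2 g/dL fall is 20% there, and less at higher baselines, so that rule would not catch it.

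**The case against.** Five arguments weigh on the other side.

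- **Covariates, pooled contrasts and subgroup tables commonly belong in an SAP, which is not shown.** This would dispose of the point if the protocol were silent. It is not: section 11.1 names the Hb test. Nothing there rules out further analyses, so the point is that a better method than the stated one is available at almost no cost, not that detail is missing.
- **Baseline is already used.** A reader might infer that Hb is compared with no regard to baseline. That is wrong, because percent change from baseline is one of the two tested outcomes. Only a covariate-adjusted model is absent, and at 20 vs 20 it adds about 4 to 8 percentage points of power.
- **Individual falls are monitored.** A reader might infer that a haemolysis signal would be lost altogether. The rule for falls above 40%, haematological AE reporting, the haemolysis checks and DSMB review do not support that. What stands is that smaller falls escape the 40% rule and are diluted in the means.
- **Matched contrasts are deliberate, and serious falls may be unlikely.** Section 4.2 defines pairs by backbone, and the effect of PQ with ASAQ or ALAQ is described as unknown, so pooling can only supplement them. Section 12.2.2 also cites studies in deficient individuals that found no clinically relevant Hb reduction. The assumed 2 g/dL is therefore illustrative; smaller falls would be still harder to see in the means.
- **Withdrawal is discretionary.** A reader might infer that section 8.2 removes affected participants from the safety analysis. It does not say so, earlier values remain, and section 9 expects the largest fall within 7 days. Later values could still be lost for a reason related to the outcome, so this is secondary.

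**Conclusion.** The point holds in limited form. The mean Hb comparison fixed in section 11.1 is a weak instrument for the risk the protocol describes, and the genotype that would locate that risk is not used for Hb. The dilution to 10–15%, and the expectation of 2–3 deficient participants per arm, follow from the document alone. All Hb power figures rest on assumed SDs, correlations and effect sizes.

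It is tempting to conclude that pooling and adjustment would solve the problem, because power of 60–96% looks strong. That range is for a general 0.6 g/dL difference. For a fall confined to deficient participants the same model reaches 14–24%, against 9–13% as planned. Only the genotype table addresses that signal, and with so few deficient participants it can only describe. The planned t-tests are poorly matched to this question but not invalid. This is a change that should be made; it is not a fatal flaw.

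**What to change.** 1. In section 11.1, replace the between-arm Hb t-tests by a baseline-adjusted model (ANCOVA or repeated measures) that keeps each matched contrast of section 4.2.
2. Add, as supplementary, a PQ vs no-PQ estimate pooled over ASAQ and ALAQ. It assumes a similar PQ effect on both backbones, so show the two backbone-specific estimates beside it.
3. Tabulate individual Hb change, maximum drop and falls above 40% by PQ and G6PD genotype, stated to be descriptive only.
4. In section 8.2 or 11.1, state that Hb and AE data of participants withdrawn after an AE stay in the safety analysis, and that scheduled Hb and AE data continue to be collected where the participant agrees. Clinical care does not change.

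The cost is wording and a little programming. Hb is already measured at every visit, and the day 0 genotyping sample is already in Table 6. Continued follow-up after withdrawal uses visits already scheduled.
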